8.3. Exploratory outcome

 Health related quality of life (proxy EQ-5D-5L and proxy WHODAS 2.0) at randomisation (day 0)¹

8.4. Safety outcomes

Hypercalcaemia at day 5

- Self-reported falls, fractures until day 90
- New episodes of kidney stones

¹ UK-specific outcome no longer collected for patients recruited post-SA5 implementation

8.5. Schedule of Assessment

ASSESSMENT	Screening	Enrolment Baseline	Begin Daily Dose	Follow-Up	Follow-Up	Follow-Up	Follow-Up	Follow-Up
ASSESSMENT	Day -3 to Day 0	Day 0	Day 1	Day 5	Day 12	Day 28	Day 90	Month 12
Time window (days)				±2	±2	+4	±14	±30
25(OH)D	Х							
Eligibility assessment	X	X						
Informed consent	X	X						
Randomisation		X						
Baseline demographics		Х						
SAPS III		Х						
TISS 28		X						
Charlson comorbidity index		Х						
Adverse events								
Mortality ¹				Х		X ²	Х	Х
Serum calcium	Х	Х		Х		X3		
Falls							X	
Fractures							X	
New episodes of nephrolithiasis							X	
Number of organ failures ¹		Х		Х				
Infections requiring antibiotics ¹							Х	
Hospital and ICU readmission ¹							X	
Intervention								
Loading dose 540,000 IU or matched placebo		Х						
Daily dose 4,000 IU or matched placebo			X	Х	X	Х	Х	
Outcome measures								
SOFA		Х		Х				
qSOFA		Х						
Discharge destination							Х	
Katz Activity of Daily Living		Х					Х	
NHS digital, ONS/HES data								Х
(vitamin D metabolic profiling (optional research)		X ⁴		X ⁴	X ⁴			
UK specific outcomes								
Health related quality of life (proxy EQ-5D-5L)		X ^{5,6}				X ^{5,6}	X ^{5,6}	X ^{5,6}
Health related quality of life (EQ-5D-5L)		X ⁵				X ⁵	X ⁵	X ⁵
Disability assessment (proxy WHODAS 2.0)		X ^{5,6}				X ^{5,6}	X ^{5,6}	X ^{5,6}
Disability assessment (WHODAS 2.0)		X ⁵				X ⁵	X ⁵	X ⁵
Health economics questionnaire						X 5	X ⁵	X5

¹ Outcome measure ² Primary outcome ³ If still an inpatient

 $^{^4}$ If patient recruited pre-SA5 implementation and consents to the sub-study 5 If patient recruited pre-SA5 implementation 6 To be used if the patient does not have capacity

8.6. Participant Withdrawal

Informed consent is defined as the process of learning the key facts about a clinical trial before deciding whether to participate. It is a continuous and dynamic process and patients should be asked about their ongoing willingness to continue participation.

Patients should be aware at the beginning that they can freely withdraw (discontinue participation) from the trial (or part of) at any time.

Types of withdrawal as defined are:

- The patient would like to withdraw from trial treatment, but is willing to be followed up
 in accordance with the schedule of assessments and via any central UK NHS bodies
 for long-term outcomes (i.e. the patient has agreed that data can be collected and
 used in the trial analysis)
- The patient would like to withdraw from trial treatment and does not wish to attend
 trial visits in accordance with the schedule of assessments but is willing to be
 followed up at standard clinic visits and via any central UK NHS bodies for long-term
 outcomes (i.e. the patient has agreed that data can be collected at standard clinic
 visits and used in the trial analysis, including data collected as part of long-term
 outcomes)
- The patient would like to withdraw from trial treatment and is not willing to be followed up in any way for the purposes of the trial and for no further data to be collected (i.e. only data collected prior to the withdrawal can be used in the trial analysis)

The details of withdrawal (date, reason, and type of withdrawal) should be clearly documented in the source data.

If a patient decides to withdraw from the VITDALIZE UK Trial, the site should complete the Change of Status Form. The Change of Status Form is required to capture withdrawal relating to the UK specific outcomes.

A Study Discontinuation Form should be completed in ClinCase for the following reasons:

- Completed study alive
 - o Final visit at 12 months done
 - This also includes patients whose study medication was lost or who did not want to proceed taking the medication

- Death
 - Documented death before/at final visit (12 months +-30 days)
- · Lost to follow-up
 - o No further information can be obtained at final visit (12 months +-30 days)
- Withdrawn consent
 - o Full withdrawal of consent, no further data will be collected
 - o Data are used until withdrawal is documented
- Other reason
 - o Other individual circumstances may apply

9. ADVERSE EVENT REPORTING

9.1. Reporting Requirements

The collection and reporting of Adverse Events (AEs) will be in accordance with the Medicines for Human Use Clinical Trials Regulations 2004 and its subsequent amendments. The Investigator will assess the seriousness and causality (relatedness) of all AEs experienced by the patient. This should be documented in the source data with reference to the approved reference safety information (refer to Section 9.6).

9.2. Adverse Events

Patients randomised to VITDALIZE UK will, by nature of their condition, be critically ill and most of the resulting AEs (whether serious or not) will be anticipated in the sense that they are recognised and accepted complications of critical illness. Additionally the safety profile of the trial intervention is well established so although the severity and causality of all AEs should be recorded in the patient's medical notes, a strategy of targeted reporting (to the Sponsor) of AEs will not compromise the safety of patients. Refer to Section 9.3 for guidance on SAE reporting procedures.

9.3. Serious Adverse Events (SAE)

9.3.1. Events that are excluded from reporting

At whatever time they occur during an individual's participation (from randomisation until 15 days post last IMP administration), the following are 'protocol exempt' SAEs:

• Events related to the patient's pre-existing condition(s)

All events which meet the definition of 'serious' must be recorded in the patient's medical notes, including causality, throughout the patient's time on the trial.

9.3.2. Events that do not require expedited (immediate) reporting

The below events are regarded as expected SAEs for the purpose of the trial and recorded on the follow-up Case Report Forms (CRF). If mortality is related to a pre-existing condition, it should be documented on the Study Discontinuation Form and Change of Status Form. If mortality is deemed to have causal relationship with the intervention it should be reported in an expedited manner as outlined in Section 9.3.3.

Table 1: Non-expedited events

Event	CRF		
Mortality ¹	Study Discontinuation Form, Change of Status Form and		
Wortanty	SAE Form ⁴ (if applicable)		
Change in organ dysfunction (number of organ failures)	Day 0; Day 5 Form; Adverse Events Form ⁵		
Hypercalcaemia ²	Adverse Events Form ⁵		
New episodes of nephrolithiasis ³	Adverse Events Form ⁵		
Falls and fractures	Adverse Events Form ⁵		
Infections requiring antibiotics treatment	Day 90 Form		

¹ Mortality due to a pre-existing condition requires documenting on the Study Discontinuation Form located on the eCRF and Change of Status Form

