9.3.3. Events that require expedited (immediate) reporting

The research team at site will report all SAEs that are not defined in Sections 9.3.1 and 9.3.2 in an expedited manner. The research team at site are required to report expedited SAEs using both the:

- eCRF (minimum dataset)
- Paper SAE Form

The additional paper SAE form has been included to ensure that appropriate key data points (from a UK-regulatory perspective) are captured. Please refer to Section 9.5.2 for more detail on reporting expedited SAEs.

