9.5.2. Serious Adverse Events

Sites should report SAEs which are NOT classed as 'protocol exempt' or those that can be reported in non-expedited manner (as defined in Sections 9.3.1 and 9.3.2), to the VITDALIZE UK Trial Office within 24 hours of site being made aware of event.

Table 2: Reporting SAEs

On becoming aware that a patient has experienced a SAE, the PI or delegate should report the SAE to their own Trust in accordance with local policies and to the VITDALIZE UK Trial Office in accordance with the VITDALIZE UK Protocol. In addition, the research team at site will be required to respond to any related queries raised by the VITDALIZE UK Trial Office as soon as possible.

The PI (or medically qualified delegate) will assess relatedness and severity of the SAE. The following categories will be used to define the relatedness (causality) of the SAE:

Category	Definition	Causality
Definitely	There is clear evidence to suggest a causal relationship, and other possible contributing factors can be ruled out	
Probably	There is evidence to suggest a causal relationship, and the influence of other factors is unlikely	Related
Possibly	There is some evidence to suggest a causal relationship, however, the influence of other factors may have contributed to the event (e.g. the patient's clinical condition, other concomitant events or medication)	
Unlikely	There is little evidence to suggest there is a causal relationship; there is another reasonable explanation for the event (e.g. the patient's clinical condition, other concomitant events or medication)	Unrelated
Not related	There is no evidence of any causal relationship	

To report an expedited SAE to the VITDALIZE UK Trial Office, the PI or delegate must complete, date, and sign the trial specific VITDALIZE UK SAE forms. The completed form should be uploaded on the eCRF and sent to the VITDALIZE UK Trial Office using the contact details listed below as soon as possible and no later than 24 hours after first becoming aware of the event:

Completed SAE Forms can be sent to the VITDALIZE Trial Office on:

Via email: [contact]

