9.6. Reporting Procedure – BCTU Trials Office

Proof of receipt will be provided to the site within 1 working day. The SAE reference number will be quoted on all correspondence and follow-up reports regarding the SAE and filed with the actual SAE in the TMF.

On receipt of an SAE Form, the CI or delegate will determine the seriousness and causality of the SAE. An SAE judged by the CI or delegate(s) to have a reasonable causal relationship with the trial medication will be regarded as a Serious Adverse Reaction (SAR). The causality assessment given by the PI will not be downgraded by the CI or delegate(s). If the CI or delegate(s) disagrees with the PI's causality assessment, the opinion of both parties will be documented, and where the event requires further reporting, the opinion will be provided with the report.

The CI or delegate(s) will also assess all expedited SAEs for expectedness. If the event meets the definition of a SAR that is unexpected (i.e. is not defined in the approved version of the Reference Safety Information (RSI): Section 4.8 Undesirable Effects - Summary of Product Characteristics (SPC) Cholecalciferol – Oleovit D3 14,400 IU/ml oral drops, solution, December 2015 it will be classified as a Suspected Unexpected Serious Adverse Reaction (SUSAR).

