9.9. Data Monitoring Committee

The independent Data Monitoring Committee (DMC) will review all SAEs.

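### Serious, non-fatal Table 1 events judged related to the trial drug have no written route to SAR/SUSAR classification, because the causality override in 9.3.2 covers mortality only

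*Protocol*

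**What the plan says.** Section 9.3.2 of the Protocol introduces Table 1 with "The below events are regarded as expected SAEs for the purpose of the trial and recorded on the follow-up Case Report Forms (CRF". The six rows are mortality, change in organ dysfunction, hypercalcaemia, new nephrolithiasis, falls and fractures, and infections needing antibiotics.

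One causality exception follows: "If mortality is deemed to have causal relationship with the intervention it should be reported in an expedited manner as outlined in Section 9.3.3". In Table 1 the mortality row names an SAE Form and carries footnote 4, which asks for that form when the event is causally related. Four rows point to the Adverse Events Form with footnote 5, which states that this form is not an SAE form. Infections go to the Day 90 Form.

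Section 9.3.3 sets the scope of expedited reporting: "The research team at site will report all SAEs that are not defined in Sections 9.3.1 and 9.3.2 in an expedited manner". Section 9.5.2 repeats the exclusion. Under 9.6 the CI determines seriousness and causality on receipt of an SAE Form, and "will also assess all expedited SAEs for expectedness", using Section 4.8 of the SPC as the reference.

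Section 9.3.1 also exempts "Events related to the patient's pre-existing condition(s" from reporting. Section 9.9 says: "The independent Data Monitoring Committee (DMC) will review all SAEs".

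**The concern.** A reporting exemption for anticipated events in critical illness is reasonable, and 9.2 gives the reason for it. Such an exemption should give way when the investigator thinks that the drug caused a serious event. Here it gives way for deaths only. Three of the exempt rows (hypercalcaemia, kidney stones, falls and fractures) are the trial's own safety outcomes in 8.4, so the exemption covers events for which a drug cause is most likely to be considered.

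At stake is case-level pharmacovigilance: whether a serious event judged related is looked at by the CI, classified as a SAR, tested for expectedness and, if unexpected, reported within the time limits of 9.7.1. The documents that depend on that stream (the DSUR, DMC review, Sponsor and manufacturer reporting) would also be incomplete by their own description.

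**Working it through.** No arithmetic produces this point. The check is to follow each Table 1 row through the text for one case: the event is serious, and the PI rates it possibly, probably or definitely related (the three categories that count as related in 9.5.2).

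| Table 1 row | Form in Table 1 | Causality override? | Excluded by 9.3.3 and 9.5.2? | Reaches CI review in 9.6? |
|---|---|---|---|---|
| Mortality | Study Discontinuation, Change of Status, SAE Form if applicable | Yes (9.3.2 text, footnote 4) | No, if related | Yes |
| Organ dysfunction | Day 0, Day 5, Adverse Events Form | No | Yes | No written route |
| Hypercalcaemia | Adverse Events Form | No | Yes | No written route |
| Nephrolithiasis | Adverse Events Form | No | Yes | No written route |
| Falls and fractures | Adverse Events Form | No | Yes | No written route |
| Infections | Day 90 Form | No | Yes | No written route |

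Rows with a route: 1 of 6. Rows without: 6 − 1 = 5.

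**Does another section close the gap?** Sections 9.1 and 9.2 have the site record causality for all AEs in the source data or medical notes. Section 9.5.1 sends the listed events to the Trial Office as AEs. Neither turns a judgement of related into an SAE Form, which is what starts the review in 9.6.

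**Downstream sections.** Section 9.7.2 has the DSUR cover all SAEs, 9.9 has the DMC review all of them, and 9.10 sends all of them to the Sponsor. A serious event held only on a form that is declared not to be an SAE form does not enter that stream.

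**Two meanings of expected.** Section 9.3.2 fixes the label by list. Section 9.6 decides it against SPC Section 4.8, and the Definitions table makes it depend on nature or severity. A list without a severity criterion cannot settle the second.

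**Section 9.3.1.** The exemption turns on a link to a pre-existing condition. The Possibly category in 9.5.2 reads: "There is some evidence to suggest a causal relationship, however, the influence of other factors may have contributed to the event", and it gives the patient's clinical condition as an example of such a factor. The text does not say which rule prevails when both apply.

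**Exposure.** This protocol governs UK patients: about 800 (Trial Summary) or 600 (14.1). With 1:1 allocation, 600/2 = 300 to 800/2 = 400 receive vitamin D. The documents give no rate of serious, related Table 1 events. Each assumed 1% would be 0.01 × 300 = 3 to 0.01 × 400 = 4 such patients. The gap in the text does not depend on this figure.

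**The case against.** The strongest reply is that little is lost. Hypercalcaemia at day 5, kidney stones, falls and fractures are safety outcomes (8.4), compared between arms with a mixed effects binomial model (14.3.4). Organ failures and infections are secondary outcomes (8.2). The DMC receives accumulating analyses (15.6), and a significant safety issue goes at once to the MHRA, REC and Sponsor (9.7.4). This stands. A reader might infer that a harm signal would be undercounted in the trial's safety conclusions. The documents do not support that, because the between-arm comparison needs neither an SAE Form nor a causality opinion.

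Nor is it right that such events can never reach the CI, since a fatal case judged related enters through the mortality exception. Nor do the documents show that any SUSAR would be missed. If SPC Section 4.8 covers these events in nature and severity, none would be; that text is not at hand.

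The flowchart that makes up the opening of 9.5 is not shown and may contain a causality step. That lowers confidence slightly. If it does, it would conflict with the text of 9.3.2, 9.3.3 and 9.5.2, and they would still need reconciling. Footnote 4 is worded generally, but the body text of 9.3.2 names mortality alone.

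On 9.3.1, the natural reading is an event attributed to the underlying condition rather than to the drug. The overlap with Possibly is therefore an ambiguity, not a clear error.

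On the word expected, 9.3.2 adds that it is meant for trial purposes, and 9.2 explains the sense, so the clash with 9.6 is partly one of terms. It still matters, because 6.5 ties emergency unblinding to events that are serious, unexpected and related, and refers the site to 9.3.

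**Conclusion.** The point holds for serious, non-fatal Table 1 events that the PI judges related. In five of six rows the printed text gives them no route to CI causality review, expectedness assessment or SAR/SUSAR classification, and this is inconsistent with 9.7.2, 9.9 and 9.10. The mortality exception shows that the authors accept the principle that relatedness overrides the exemption; it was not carried to the other rows.

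The consequence is loss of individual-case classification, not loss of the events as data or of the comparison between arms. How many cases are affected, and whether any would be SUSARs, cannot be determined from the document. The conclusion rests on the printed text of Section 9 and on the 9.5 flowchart not overriding it.

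**What to change.** 1. In 9.3.2, extend the mortality exception to every row of Table 1. Suggested wording: *The exemption applies only to events that the PI assesses as unlikely to be related or not related. Any serious event assessed as possibly, probably or definitely related is reported on the SAE Form under Section 9.3.3.* Attach footnote 4 to all rows, and carry the same condition into 9.3.3 and 9.5.2.
2. In 9.3.1, state that the pre-existing-condition exemption does not cover an event that is also judged related to the IMP.
3. In 9.3.2, replace the label of expected SAEs with anticipated events not needing expedited reporting, so that expectedness is judged only against the RSI in 9.6. Align 9.5.1, which uses the same label.
4. Check the 9.5 flowchart against the revised text.

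The cost is a wording amendment, a notice to sites and a small number of extra SAE Forms. Because PIs are blinded, the forms will come from both arms: each assumed 1% of 600 to 800 UK patients adds 6 to 8. They are limited to serious events for which the PI already has to record a causality judgement.

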9.3.3. Events that require expedited (immediate) reporting

The research team at site will report all SAEs that are not defined in Sections 9.3.1 and 9.3.2 in an expedited manner. The research team at site are required to report expedited SAEs using both the:

- eCRF (minimum dataset)
- Paper SAE Form

The additional paper SAE form has been included to ensure that appropriate key data points (from a UK-regulatory perspective) are captured. Please refer to Section 9.5.2 for more detail on reporting expedited SAEs.

9.3.4. Monitoring pregnancies for potential Serious Adverse Events

There is an identified risk of congenital anomalies or birth defects in the offspring of patients that may occur as a result of their participation in the trial. The outcome of pregnancies of patients will therefore be monitored in order to provide SAE data on congenital anomalies or birth defects.

Pregnant or women who are lactating are excluded from the trial. However, in the event that a patient becomes pregnant during the SAE reporting period a Pregnancy Notification Form will be completed and returned to the VITDALIZE UK Trials Office. If a female patient is found to be pregnant whilst in the trial, they will be advised to stop taking their trial medication and with their permission, they will continue to be followed up per the trial protocol and included in the analysis per intention to treat. Details of the outcome of the

² Where persistent hypercalcemia is present, it is a clinical recommendation for a parathyroid hormone (PTH) test to be performed before continuing with the trial medication

³ Decrease/increase in kidney function, specifically CKD 4 (eGFR <30mL/min/1.73m²)

⁴ SAE form to be completed if there is a causal relationship to intervention

⁵ Please note that the Adverse Events Form is **not** a SAE Form

pregnancy should be captured on a Pregnancy Notification Form. A congenital anomaly, birth defect, foetal death or stillborn will be reported as an SAE and in compliance with the section on SAEs.

There is no risk identified from male patients who take vitamin D3 whose partner subsequently becomes pregnant.

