 - Cost per quality-adjusted life year gained 1 year after randomisation and at end of life

Exploratory outcome:

 Health related quality of life (proxy EQ-5D-5L and proxy WHODAS 2.0) at randomisation (day 0)¹

Safety outcomes

Hypercalcaemia up to day 5 (48 hours tolerance)/during ICU stay

- Self-reported falls, fractures until day 90
- New episodes of kidney stones until day 90

VITDALIZE UK PROTOCOL

 $^{^{\}rm 1}$ UK-specific outcome no longer collected for patients recruited post-SA5 implementation

Trial Schema

[figure not shown]

TABLE OF CONTENTS

1.	BACKGROUND AND RATIONALE	23
1.1.	Background	23
1.2.	Trial Rationale	24
1.2.1.	. Justification for patient population	26
1.2.2.	. Choice of intervention	27
2.	AIMS AND OBJECTIVES	28
2.1.	Aims and Objectives	28
3.	TRIAL DESIGN AND SETTING	29
3.1.	Trial Design	29
3.2.	Trial Setting	29
3.3.	Additional Sample Collection for Future Research (Optional)	29
3.4.	Assessment of Risk	29
4.	ELIGIBILITY	31
4.1.	Inclusion Criteria	31
4.2.	Exclusion Criteria	31
4.3.	Co-enrolment	32
5 .	CONSENT	33
5.1.	Patients who lack capacity to consent for themselves	34
5.2.	Patients transferred to non-VITDALIZE UK sites	35
6.	RECRUITMENT, ENROLMENT AND RANDOMISATION	36
6.1.	Recruitment	36
6.2.	Enrolment and Screening	36
6.3.	Randomisation	37
6.4.	Informing the patient's General Practitioner (GP)	38
6.5.	Blinding	38
7 .	TRIAL TREATMENT / INTERVENTION	40
7.1.	Treatment(s) and Dosing Schedule	40
7.1.1.	. Justification of dosing	40
7.2.	Drug Interaction or Contraindications	40
7.3.	Accountability Procedures	41
7.4.	Concomitant Vitamin D Supplementation	41
7.5.	Cessation of Treatment / Continuation after the Trial	42
7.6.	Treatment Supply and Storage	42
7.6.1.	. Treatment Supplies	42
7.6.2.		
7.6.3.	Drug Storage	43
8.	OUTCOME MEASURES AND TRIAL PROCEDURES	44
8.1.	Primary Outcome	47
8.2.	Secondary Outcomes	47
8.3.	Exploratory outcome	47

8.4.	Safety outcomes	47
8.5.	Schedule of Assessment	48
8.6.	Participant Withdrawal	49
9.	ADVERSE EVENT REPORTING	51
9.1.	Reporting Requirements	51
9.2.	Adverse Events	51
9.3.	Serious Adverse Events (SAE)	51
9.3.1.	Events that are excluded from reporting	51
9.3.2.	Events that do not require expedited (immediate) reporting	51
9.3.3.	Events that require expedited (immediate) reporting	52
9.3.4.	Monitoring pregnancies for potential Serious Adverse Events	52
9.4.	Reporting period	53
9.5.	Reporting procedure – at site	53
9.5.1.	Adverse Events	53
9.5.2.	Serious Adverse Events	53

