8. OUTCOME MEASURES AND TRIAL PROCEDURES

Screening - Day -3 to 0

- Vitamin D analysis
- Eligibility
- Informed consent

Please note, details of the screening assessment have been described earlier in Section 6.2.

Baseline - Day 0

The patient receives the loading dose of the allocated intervention (vitamin D or placebo) and the following is recorded.

- Age
- Sex
- ICU admission diagnosis
- ICU type (medical, surgical, neurological, cardiac)
- Charlson comorbidity index (based on co-morbidities on ICU admission)
- Simplified Acute Physiology Score (SAPS III)
- Therapeutic Intervention Scoring System (TISS 28)
- SOFA score (on admission to ICU)
- Number of organ failures
- Katz Activities of Daily Life (prior to ICU admission)
- Serum calcium
- If applicable¹, patient health-related quality of life questionnaire (EQ-5D-5L and WHODAS 2.0, proxy if patient does not have capacity)
- If applicable², blood sample for future research (pre-intervention)

Please note, if there has been a >24-hour delay since eligibility was confirmed, eligibility must be re-assessed prior to the patient receiving the loading dose.

Please note, the day of the study medication loading dose is the start for the calculation of the time dependent outcome data.

The SOFA and SAPS III scores will also capture data on the presence of sepsis and renal dysfunction (our 2 predefined sub-groups).

Day 1

The patient begins daily dose treatment with allocated intervention for 90 days.

Day 5

- Survival status
- Serum calcium
- Treatment with allocated trial medication
- Trial medication compliance
- SOFA score and type(s) of organ support
- Presence of sepsis/infection
- Targeted adverse events (refer to Section 9.3.2)
- If applicable², blood sample for future research

Day 12

• If applicable², blood sample for future research

Day 28

- Survival status (primary endpoint 28-day mortality)
- Serum calcium (if still in hospital)
- Targeted adverse events (refer to Section 9.3.2)
- Treatment with allocated trial medication
- Trial medication compliance
- If applicable¹, patient health-related quality of life questionnaire (EQ-5D-5L and WHODAS 2.0, proxy if patient does not have capacity)
- If applicable¹, health economics questionnaire

Day 90

- Survival status
- · Katz Activities of Daily Living
- Targeted adverse events (including self-reported infections requiring antibiotics, self-reported falls and fracture, hospital, and ICU admissions)
- Discharge destination

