14.3.4. Secondary Outcome Measures

ICU, hospital mortality, 90-day mortality and 1-year mortality will be analysed using the same methods as described for the primary outcome. For any other secondary outcomes that are continuous, these will be analysed using mixed effects linear regression model. The safety outcomes, (hypercalcemia on day 5, new kidney stones, self-reported falls, and fractures until day 90) will be analysed as binary variables and compared using a mixed effects binomial model.

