14.3.5. Subgroup Analyses

The effect of high dose vitamin D versus placebo will be evaluated in the following *a priori* subgroups: i) patients with sepsis (admission diagnosis) vs non-sepsis (based on the evidence that vitamin D has antimicrobial properties that may benefit this population in particular (16); ii) kidney function, CKD 4 (eGFR<30mL/min/1.73m2) or lower vs higher (based on the possible effect of pre-existing CKD and VDD on increased mortality and alternate metabolism of vitamin D3 (cholecalciferol); iv) COVID-19 or Non-COVID-19 patients.

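### Footnote 3 to Table 1 describes new nephrolithiasis as a change in kidney function (eGFR <30) and not a stone; the hypercalcaemia window also differs between the summary and the analysis

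*Protocol*

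**What the plan says.** **Kidney stones.** Table 1 in Section 9.3.2 sets out the events that sites record without expedited reporting. One row is "New episodes of nephrolithiasis", entered on the Adverse Events Form and marked with footnote 3. The footnote is printed after a page break, within the text of Section 9.3.4, and reads "Decrease/increase in kidney function, specifically CKD 4", with eGFR below 30 mL/min/1.73m² in brackets. It does not mention stones.

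Elsewhere the outcome is a stone:
- the trial summary has "New episodes of kidney stones until day 90";
- Section 8.4 has "New episodes of kidney stones", without an end date;
- the schedule in Section 8.5 has a nephrolithiasis row ticked at day 90;
- Section 14.3.4 names the safety outcomes to be compared as binary variables: "hypercalcemia on day 5, new kidney stones, self-reported falls, and fractures until day 90".

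**Hypercalcaemia.** The trial summary has "Hypercalcaemia up to day 5 (48 hours tolerance)/during ICU stay". Section 8.4 gives day 5 only, as does Section 14.3.4. Calcium is also scheduled at day 28 for patients still in hospital (Sections 8 and 8.5). Hypercalcaemia is a Table 1 event, and Section 9.4 keeps targeted events reportable until 15 days after the last dose.

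**The concern.** The only text that explains to sites what the nephrolithiasis row means describes something else. Intensive care patients can have an eGFR below 30 for reasons unrelated to stones, including disease present before randomisation. If such patients are entered under the stone row, the comparison of new kidney stones no longer measures stones, and a real difference between arms would be diluted by unrelated entries.

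The protocol itself treats stones and hypercalcaemia as risks of the intervention: the explanation of the exclusion criteria in Section 4.2 puts both among the conditions that raise the risk of side effects from high-dose vitamin D. These are therefore two safety outcomes a reader of the results will look for. If the hypercalcaemia window is not fixed, the published outcome could follow either the summary or the analysis section, and the two count different events.

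**Working it through.** No figure in the protocol is in dispute, so the check is mainly a comparison of texts.

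**1. Is footnote 3 attached to the right row?** Five markers appear in Table 1. Footnote 1 (deaths from a pre-existing condition) fits the mortality row. Footnote 2 (persistent hypercalcaemia) fits the hypercalcaemia row. Footnotes 4 and 5 concern the SAE form and the Adverse Events Form, and fit where those forms are named. Only footnote 3 does not fit its row. A shift in numbering or in text extraction is therefore unlikely; the content of this one footnote is wrong for its row.

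**2. Where might the wording come from?** Section 14.3.5 defines a subgroup as "kidney function, CKD 4 (eGFR<30mL/min/1.73m2) or lower vs higher". The threshold is the same, so a renal definition placed on the wrong row is the likeliest explanation. That is an inference.

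**3. What would a literal reading record?** The footnote covers a decrease or an increase in function, although only a decrease can newly bring a patient below 30. The exclusion criteria in Section 4.2 contain no eGFR limit, and Section 14.3.5 expects patients below 30 to be enrolled. A patient who enters with eGFR below 30, or falls below it, could thus be entered as a new stone. Those entries would feed the binary variable named in Section 14.3.4.

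**4. The hypercalcaemia texts side by side.**

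| Place | Window |
|---|---|
| Trial summary | up to day 5 with 48 hours' tolerance, or during the ICU stay |
| Section 8.4 | day 5 |
| Section 14.3.4 | day 5 |
| Section 8.5, day-5 visit | ±2 days |

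The 48-hour tolerance agrees with the ±2-day visit window. What remains unreconciled is a period up to day 5 against a single time point, and the added ICU-stay period. The slash in the summary does not say how its two parts combine.

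**5. Exposure at each calcium sample, for context (doses from Section 7.1).**
- Stated total: 540,000 + 90 × 4,000 = 900,000 IU, which reproduces the protocol's figure.
- By day 5, counting days 1 to 5: 540,000 + 5 × 4,000 = 560,000 IU; 560,000/900,000 = 62% of the total, with 5/90 = 6% of maintenance doses.
- By day 28: 540,000 + 28 × 4,000 = 652,000 IU; 652,000/900,000 = 72%.

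A day-5 comparison comes after the loading dose but before most of the maintenance period. The choice of window therefore changes what is measured.

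**The case against.** **The row label speaks for itself.** A site filing renal impairment as a stone must override the label, and Table 1 has a separate row for organ dysfunction where acute renal failure can go. The schedule has no separate eGFR or creatinine assessment that would prompt such entries. This stands as a reason to expect only some misfiling. It does not remove the contradiction, because the footnote is operative reporting text.

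**The effect may be small or large.** A reader might infer that the stone comparison turns into a renal failure comparison. Suppose, purely as an assumption, true stone rates of 0.5% and 1.0% and eGFR below 30 in 10% to 30% of patients in each arm. If every such patient were misfiled, the recorded risk ratio would fall from 2.0 to (10 + 1.0)/(10 + 0.5) = 1.05 or (30 + 1.0)/(30 + 0.5) = 1.02. If 5% were misfiled, it would be (0.5 + 1.0)/(0.5 + 0.5) = 1.50 or (1.5 + 1.0)/(1.5 + 0.5) = 1.25. None of these rates is in the protocol, so no size can be claimed. Even with perfect recording, 0.5% against 1.0% with 1,200 per arm has only about 29% power (normal approximation). Correction makes the data valid but does not make the test sensitive.

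**Later calcium is not shown to be discarded.** A reader might infer that day-28 calcium goes unused and that hypercalcaemia after day 5 is missed. The text does not support that. Sections 14.2 and 14.3.1 commit to using all available data, Section 14.2 leaves detail to the SAP, and later events are reportable as targeted events. What stands is narrower: the one named comparison uses day 5, and the summary states something wider.

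**A pooled outcome would bring its own bias.** Counting any raised value to day 28 would give longer-stay patients more chances to be positive, and day-28 calcium exists only for inpatients. Length of stay and mortality may differ by arm. This objection stands, and the fix avoids such an outcome.

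**Conclusion.** Footnote 3 is wrong as written. It describes a renal-function event under a row, an outcome and a planned comparison that all concern kidney stones. The contamination it could cause is real in direction but cannot be sized from the protocol, since it depends on how many sites apply the footnote and how many of their patients have eGFR below 30.

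The hypercalcaemia inconsistency is genuine but narrower: the trial summary stands against Sections 8.4 and 14.3.4, which agree with each other. Which window is clinically right is not judged here; the passages must be reconciled.

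Both matters affect the safety outcomes only.

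**What to change.** 1. Remove or correct footnote 3 so that the event recorded under nephrolithiasis is the new kidney stone named as the outcome. If eGFR below 30 is to be captured, give it its own renal entry.
2. Send a short note to sites, and re-check the nephrolithiasis entries already made against source. Re-code any that are renal-function events before the comparison is run.
3. Use one hypercalcaemia window in the trial summary, Section 8.4 and Section 14.3.4. State the end date for stones in Section 8.4 to match the summary.
4. If day 5 remains the compared time point, summarise later hypercalcaemia (targeted event reports and day-28 inpatient calcium) by arm with the numbers tested, without pooling it into an any-value outcome.

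The cost is a wording amendment, a site note and minor re-coding. The day-28 summary will cover inpatients only, so it is descriptive.
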